4.1.1.1 Participant Selection Criteria

All Port Colborne residents meeting the following criteria will be eligible to be included in this study, regardless of their primary language or literacy levels.

4.1.1.1.1 Inclusion Criteria

Participants may be included in the study if ALL of the following criteria apply:

- 1) They have understood and signed an informed consent form.
- 2) They are 12 years of age or older.
- 3) They live within Port Colborne boundaries.

4.1.1.1.2 Exclusion Criteria

Participants will be excluded from the study if they cannot comply with the study procedures.

Participants may not be included in the skin sensitivity assessment if they:

1. Have had topical corticosteroids applied to patch test sites within 24 hours of the test date,
2. Have taken oral corticosteroids at a dose equivalent to greater than 15 mg of prednisone within one week of test date,
3. Have had injectable corticosteroid within one month of testing,
4. Have taken oral cyclosporine within one week of testing,
5. Have one or more patch test sites not free of dermatitis, or any other inflammatory skin condition (e.g. psoriasis, sunburn),
6. Are pregnant,
7. Are not available for the application or reading of the patch tests, or

8. Cannot keep the dermatological patch test dry for 96 hours (this includes keeping the test sites free of excessive perspiration that may effect the outcome of the test or cause the patch to detach from the skin).

4.1.1.2 Withdrawal from Study

Individuals may withdraw from participation in the study at any time for any reason. If, for any reason, an individual chooses not to complete the study, partial responses may be used and analyzed. Additional subjects will be sampled to compensate for study “drop-outs”.

4.1.2 Geographic Areas Defined by Level of Exposure

The City of Port Colborne will be divided into five strata or categories (see Appendix 11.6). These categories will be based on approximate estimates of levels of exposure within the city. These strata ensure that each subgroup of the population is represented and that areas of interest can be “over-sampled.” They also allow for internal comparisons within the city to be made (Kelsey et al., 1996). The first area is south of Clarence St. (included) and bounded by the Welland Canal and Augustine Rd. The second area is north of Clarence St. (excluded), and bounded by Minor Rd. and the Welland Canal (includes Rosedale Subdivision). The third area is north of Lake Rd. (included), south of Durham (included), bound by Welland St. and Davis St.. The fourth area is south of 2nd Concession, north of Durham (excluded), bounded by Welland and Snider Rd.. All other areas within the boundaries of Port Colborne not mentioned above, will contribute to a fifth category which will consist largely of rural residences.

4.1.3 Randomization of Subjects

In general, a sample consists of the sampling units chosen from the population eligible to be included. The sampling unit is the unit around which the sampling procedure is planned, and in this study, the unit will be defined as the individual. The sampling frame is the list of all the sampling units in the population. A list of all residential telephone numbers that are publicly listed will be used in this study. This phone list is sorted by area code, and includes phone, name and address information for roughly 6,700 households. Based on the most recent aggregate data from Canada Post, this represents 85.3% (6,700/7,856) of households in Port Colborne. The sampling method is the way in which the sampling units are chosen from the sampling frame. As described above, the sampling method for this study will be a stratified random sampling approach. For stratification, the sampling frame will be divided into five geographic areas categorized by level of exposure to the CoCs. By assigning a random number to each telephone listing within each stratum and then sorting these listings by this random number, the sorted listings can be used to randomly select households for inclusion in the study. Within each household, participants will be randomly selected taking into account the number of residents. Specifically, for a household with r residents, the k th oldest resident will be chosen where k is a random number between 1 and r . The telephone interviewers will be supplied with tables of random numbers for households ranging from sizes of 2 to 10 to select a value for k .

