in common, and a sample is drawn from within each stratum. In this study, the strata will be defined as geographic areas categorized by approximation to level of exposure to the chemicals of concern. Stratified random sampling has several advantages over random sampling alone. First, by stratifying it can be ensured that each subgroup of the population is represented and that the carefully designed allocation of subjects can permit comparisons across strata. Second, when the population can be subdivided into groups that are more homogeneous than the population as a whole, more precise estimates of population parameters are obtained than when a random sample is taken of the whole population. This is because the variance computed for the entire sample is based on each within-stratum variance. Finally, strata can be constructed so that those that may have the largest number of individuals of interest (i.e., those with high exposures) can be sampled most heavily (Kelsey et al., 1996).

In order to perform comparisons among those individuals with potentially higher levels of exposure, an “oversampling” of residents in the Rodney Street area of Port Colborne must be done. Specifically, a proportionally higher number of people in this area will be included in the study relative to other areas of the city. The inclusion of a larger subsample in this area will allow for analysis of the results within this stratum and for comparisons to be made between this stratum and the rest of Port Colborne. Thus, even though the health questionnaire and the medical testing will not necessarily be administered to all residents of the Rodney Street area, the sample that emerges from that area will be large enough to be representative of the whole Rodney Street area in the

same way that the total sample (after weighting to adjust for oversampling) will be representative of the whole population of Port Colborne.

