In addition to the weighting that adjusts for the oversampling in the Rodney Street area, it may be necessary to make adjustments to the sample if there are more people in one demographic category or other grouping than there should be, based on the real or true distribution of these groups in the population. Using available census data, combined with the observable demographic characteristics of the created sample, mathematically-derived weighting formulas will be considered to put the final, weighted sample in line with what it should be based on the characteristics of the population. Although many mathematical adjustments are rarely required to bring a sample into line with the real distribution characteristics of a population, most studies involving large samples do require a re-weighting to some degree.

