4.1.1 Population

Port Colborne has a population of 18,450. From this population, a sample of 1,000 people who are at least 12 years of age will be randomly selected to participate in the health questionnaire and the medical testing. This sample will be chosen from a listing of all households based on phone numbers.

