10.3.3 Instructions Specific to T.R.U.E., Given Post-Application, before Subject Departs

Appendix 10.1: Health Questionnaire

CHAP Health Questionnaire

-  indicates that the questions were derived from the HRQOL-4
 -  indicates that the questions were derived from the 2000 CCHS
 -  indicates that the questions were derived from the Smith-Sivertsen paper
- ADULT indicates adult specific
CHILD indicates child specific

The following information will be kept strictly confidential. Any information that can identify you or your family will be replaced with a unique number (as viewed at the top of this page). This identifying information will be kept separately and under restricted access.

Last Name:  _____

First Name:  _____

Middle Name: _____

Current or Former Resident: **Current / Former**

Number of People in your Household: _____

ALL MEMBERS OF HOUSEHOLD (12+) ARE TO ANSWER THE FOLLOWING QUESTIONS. SOME QUESTIONS MAY NOT APPLY (CHILD OR ADULT SPECIFIC).

Demographic Information

1. What is your date of birth? DD/MM/YYYY 

2. Please indicate your sex: 
 - Male
 - Female

3. People living in Canada come from many different cultural and racial backgrounds.
Are you: 

INTERVIEWER: Read categories to respondent. Mark all that apply.

- 1 ...White?
 - 2 ...Chinese?
 - 3 ...South Asian (e.g., East Indian, Pakistani, Sri Lankan, etc.)?
 - 4 ...Black?
 - 5 ...Filipino?
 - 6 ...Latin American?
 - 7 ...Southeast Asian (e.g., Cambodian, Indonesian, Laotian, Vietnamese, etc.)?
 - 8 ...Arab?
 - 9 ...West Asian (e.g., Afghan, Iranian, etc.)?
 - 10 ...Japanese?
 - 11 ...Korean?
 - 12 ...Aboriginal Peoples of North America (North American Indian, Métis, Inuit / Eskimo)?
 - 13 Other – Specify
-
4. How tall are you without shoes on?  (offer both ways of measuring, want metres)

 5. How much do you weigh?  (offer both ways of measuring, want kg)

6. Do you consider yourself: 
- overweight?
 - underweight?
 - just about right?
7. What is your current marital status?  ADULT
- Married
 - Living Common-law
 - Widowed
 - Separated
 - Divorced
 - Single (never married)
8. Highest grade of elementary or high school completed: 
- ___ Grade 8 or lower (Quebec: Secondary II or lower)
 - ___ Grade 9 – 10 (Quebec: Secondary III or IV; Newfoundland: 1st year of secondary)
 - ___ Grade 11 – 13 (Quebec: Secondary V; Newfoundland: 2nd to 4th year of secondary)
9. Highest degree, certificate or diploma:  ADULT
- ___ No postsecondary degree, certificate or diploma

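### Drawing one resident per household gives each person a selection chance proportional to 1/r, but no household-size weight is fixed and r is not limited to residents aged 12 or older

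*Protocol*

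**What the plan says.** Protocol section 4.1.3 calls the individual the sampling unit, but the list it draws from is one of household telephone listings. Listings are put in random order within each of five areas, and "the sorted listings can be used to randomly select households for inclusion in the study". One person is then taken: "for a household with r residents", "the k th oldest resident will be chosen where k is a random number between 1 and r". No age limit is attached to r, although section 4.1.1 says that "a sample of 1,000 people who are at least 12 years of age will be randomly selected".

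On weighting, section 4.1 states that "the total sample (after weighting to adjust for oversampling) will be representative of the whole population of Port Colborne" and that "the sample that emerges from that area will be large enough to be representative of the whole Rodney Street area". It continues, "In addition to the weighting that adjusts for the oversampling in the Rodney Street area", that adjustment may be needed if a demographic or other group is over-represented, and that weighting formulas will be considered. Section 6.2.1.1 lists household size among the variables to be used for adjustment if the sample and population distributions differ. Mock Table 2 in section 6.5.1 compares mean household size with the 1996 census.

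Two other places bear on the rule. The questionnaire in Appendix 10.1 records "Number of People in your Household" without an age limit, and it is headed by an instruction that all household members aged 12 or older answer. Section 6.1.1 expects 234 female participants in the Rodney Street area (Area 3).

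**The concern.** Equal chance for households followed by one draw per household is not equal chance for people. Someone living alone is four times as likely to be chosen as a member of a four-person household in the same area. The random choice of k makes the draw fair inside the household; it does not undo the inequality between households. A weight for area oversampling corrects differences between areas and leaves this one untouched.

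The primary objective is to describe the health of residents, and section 6.1.1 sizes the study on the precision of prevalence estimates. Household size is plausibly related to age, marital status, income and exposure to others' smoke, so it can be related to the outcomes. Age and sex adjustment removes only the part of the distortion that runs through age and sex.

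The rule for r is also a fieldwork instruction. If the number of eligible residents is not recorded when the household is called, it cannot be rebuilt from a questionnaire item that counts everyone.

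**Working it through.** **1. The plan's own figure.** Section 6.1.1 assumes 65% response and 50% women, and Table 2 in that section gives 719 residents aged 12 or older in Area 3. 719 × 0.65 × 0.50 = 233.7, the stated 234. It reproduces only if every eligible resident of Area 3 is approached.

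**2. The same figure under one person per household.** Table 2 gives 365 private dwellings in Area 3. 365 × 0.65 = 237 participants, of whom 237 × 0.50 = 119 are women. If the citywide listing rate in section 4.1.3 (6,700/7,856 = 85.3%) applies there, 365 × 0.853 × 0.65 = 202 participants, about 101 women. Table 1 asks for 181 women in Area 3 for the 7%–13% nickel row, and section 6.1.1 assumes 500 subjects there for the comparison between areas.

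**3. Selection chance.** Let h_r be the share of households with r eligible residents and M the mean of r.
- Share of an unweighted sample living in size-r households: h_r.
- Share of the eligible population living in them: r·h_r/M.
- For people living alone the ratio of the two is M. Table 2 gives 16,355/7,375 = 2.22 persons aged 12 or older per dwelling, so they are over-represented about 2.2 times.

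**4. Illustrative size.** The protocol gives no household-size distribution. Three assumed splits for sizes 1 to 5, with means near 2.22:

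| Split (%) | M | Alone: sample / population | Size 4+: sample / population | E[r²]/M² |
|---|---|---|---|---|
| A: 25/40/18/12/5 | 2.32 | 25% / 10.8% | 17% / 31.5% | 6.64/5.38 = 1.23 |
| B: 30/36/19/11/4 | 2.23 | 30% / 13.5% | 15% / 28.7% | 6.21/4.97 = 1.25 |
| C: 20/50/20/8/2 | 2.22 | 20% / 9.0% | 10% / 18.9% | 5.78/4.93 = 1.17 |

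If prevalence is p₁ in people living alone and p₂ in all others, bias = (h₁ − h₁/M)(p₁ − p₂).
- p₁ = p₂: 0.
- 7.5% against 5%: 0.36, 0.41 and 0.27 points for A, B and C.
- 10% against 5%: 0.71, 0.83 and 0.55 points.

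The accuracy stated in section 6.1.1 for a 5% asthma prevalence is ±2 points at 80% confidence.

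**5. Cost of weighting by r.** The last column of the table is the design effect. For it, 500 respondents carry the information of 500/1.23 = 405, 500/1.25 = 400 and 500/1.17 = 426. Half-widths grow by its square root, 1.08 to 1.12, so ±2 points becomes about ±2.2.

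**6. Children under 12.** The footnote to Table 2 puts 85% of the community at 12 or older. If r counts everyone, up to about 15% of draws land on an ineligible child. The share is lower if, as is likely, children live in larger households, where each person's chance is smaller. Section 4.1.3 gives no rule for that event.

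**The case against.** The protocol is not blind to household size. Section 6.2.1.1 names it as an adjustment variable, mock Table 2 compares its mean with the census, and section 6.4 compares family size between participants and non-respondents. A reader might infer that only area and the usual demographics can ever be corrected, or that the protocol expects re-weighting seldom to be needed. Neither is supported: section 4.1 ends by saying that most large-sample studies need some re-weighting. These routes stand, but they are conditional on an observed mismatch, and a comparison of means is a weak trigger for a distortion already known from the design.

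The weight formula could be left to an analysis plan that is not shown. That is fair for the formula. It does not cover the selection rule, the recording of r, or the representativeness claim, all of which belong to this protocol.

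It can also be said that r means eligible residents, since section 4.1.3 begins from the eligible population. That is a reasonable intention, but the instruction to the telephone interviewers does not say so.

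A further tempting inference is that every prevalence, and the Ontario comparison, is materially wrong. The documents do not support this. The Ontario rates are standardized by age and sex, and the area comparison in mock Table 5 is adjusted for both. Large biases need steep assumed gradients. For example, prevalences of 25/20/10/8/8% over a 27/46/16/9/2% split give 18.4% instead of 15.8%. The arithmetic is right, but nothing in the protocol supplies that gradient.

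Finally, if all eligible residents of Area 3 were approached, the 1/r problem would vanish there. Section 4.1 says that not all residents of that area will necessarily be included, so this is a contradiction to settle.

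**Conclusion.** The point holds in a limited form. The unequal selection chance is certain under section 4.1.3, and the one weight the protocol commits to does not address it. Representativeness after that weight therefore does not follow, either for the city or within the Rodney Street area. Bias in a given prevalence is conditional: it arises only where the outcome still varies with household size after the adjustments applied. It is 0 to about 0.8 points on a prevalence near 5%, assuming 20–30% one-person households and up to twice the prevalence in people living alone. That lies inside the stated ±2 points but is systematic, and a larger sample does not shrink it. Two related faults stand on the text alone: r is not restricted to eligible residents, and the one-per-household rule conflicts with the Appendix 10.1 instruction and the Area 3 yield of 234 women.

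**What to change.** - In section 4.1.3 and the telephone script, define r as the number of residents aged 12 or older, and record it at the selection call for every household reached.
- In section 4.1, make r (capped if needed, for example at 4 or 5) a fixed factor in each participant's design weight, applied before the area weight and any census calibration. State that prevalence estimates use this weight. A cap trades a little residual bias for less variance.
- In section 6.1.1, restate precision with a design effect of about 1.2, or show the range 1.17 to 1.25 until the household-size distribution is known.
- Reconcile the one-per-household rule with the Appendix 10.1 instruction and with the Area 3 yield. If one person per household is kept, the Area 3 numbers fall to about 202–237 participants (101–119 women) at 65% response, and the precision and comparison claims must be revised. If all eligible residents of Area 3 are approached, section 4.1.3 must say so, r drops out of the weight there, and clustering within households needs to be allowed for.

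The cost is one line in the script, one factor in the weight, and intervals about 8–12% wider. Recording r must be settled before fieldwork, because it cannot be recovered afterwards from the questionnaire.

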4.2. Study Procedures

4.2.1 Overview

The study procedures section will describe the methodology surrounding both the health questionnaire and Medical Tests. This section will further describe the co-ordination of these two components in the Schedule of Events section.

4.2.2 Health questionnaire

The health questionnaire has five major sections: demographic information; residential, occupational, lifestyle/dietary, educational, and other exposure information; a health related quality-of-life measure; current medical health status information; and mental health information. There are some questions that will be either adult (18+) or adolescent specific. The adult-specific questions include occupational-related questions; certain demographic questions (i.e. income, educational level); and lifestyle questions (i.e. smoking status and alcohol use). The adolescent-specific questions include information on multiple residences, if applicable, and school identification, location and duration of attendance. Otherwise, the questions asked of the adolescents are the same as those of adults, with the identical objective of obtaining key exposure and general health information.

4.2.2.1 Questionnaire development and internal testing

Questions from the demographic section of the questionnaire were derived from the CCHS. Most of the questions collecting exposure information were developed under the advisement of experts in the areas of toxicology and environmental health and safety.

Questions pertaining to the smoking of cigarettes and consumption of alcohol were borrowed from the CCHS. The questions that assess quality of life came directly from the HRQOL-4 questionnaire that was developed by the CDC. There are five symptom questions within the section of the questionnaire that collects information on current medical health status. These questions were used in the work done by Smith-Sivertsen and colleagues (2000). The rest of the health related questions come from the CCHS, with a few exceptions for health outcomes of particular interest for this study. Finally, all questions on drug use and mental health again come from the CCHS.

The only identifying information collected in this questionnaire is the individual's name and date of birth. This information will be entered into the data entry application and will only be used for identifying individuals if they request their data. Otherwise, all identifying information will be permanently removed before any analyses take place.

During the development of the health questionnaire, wording was not modified for the CCHS-derived health questions, the HRQOL-4 questions, or the questions borrowed from the research done by Smith-Sivertsen et al. (2000). These are pre-existing, validated questions that require consistent phrasing so as to allow for comparisons with other datasets.

Once the health questionnaire has been finalized, questionnaires will be prepared for pre-testing. This pre-testing will also allow for data entry, handling, and analyses procedures

to be checked, and thus they will need to be in place prior to the pre-testing. The questionnaire will be pre-tested while interviewer training proceeds.

During the pre-test, the interview team will duplicate as closely as possible the procedures that will take place during the administration/fielding of the final questionnaire. While the pre-test is being conducted, progress will be closely monitored, noting and addressing any problems that arise in terms of the content or administration of the questionnaire, or the data management and analyses process.

4.2.2.2 Questionnaire administration

The questionnaire will be administered at the central study facility within the City of Port Colborne. The method of face-to-face interviewing will be used. It is preferable to phone interviews or self-administered surveys for the following reasons:

- longer surveys can be employed (this questionnaire will likely have a duration of 15-minutes to one half-hour);
- each resident can be met individually and face-to-face;
- the physical and friendly presence of the interviewer increases the possibility that respondents will complete all questions/keep going with survey;
- personal contact and rapport with the interviewer increases the commitment that the respondent feels toward the survey, and they are more likely to be willing to invest the time needed to complete the health questionnaire;
- the method is feasible because the survey is being conducted within the confines of a relatively small city;

- typically better than other methods among low-education, low-income, minority populations;
- increased quality control;
- interviewers can facilitate completion of the survey, as they will be on hand to explain the meaning of questions, etc. – they will be trained to do this in a way that minimizes bias of responses

The interview team will take all reasonable steps to ensure that residents who request an interview in languages other than English are given this opportunity. Interviewers will be made available who can translate the questions for these respondents. This removes the need for the entire questionnaire to be translated. Alternate arrangements will also be made for those who cannot visit the central study facility in Port Colborne.

